## 2. Status at the end point

- Completed
- Insufficient clinical effectiveness
- Recovery or effective
- Adverse events
- Transferred to other hospital/department
- Lost to follow-up
- Others

### 8.3.7. Confirmation of survival

The survival status until the end date of observation period in each booklet (or until the first visit date after discontinuation of this drug) should be recorded. In the case of death, the date of death and cause of death [ cardiovascular event, or others (including unknown) ] should be recorded.

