### 8.3.8. Adverse events

Occurrence of adverse events from the start date of administration of this drug to the end date of observation period (or first visit date after the date of discontinuation of this drug) should be confirmed and the following information should be recorded.

Also, further investigation should be separately conducted, if deemed necessary by Sponsor for patients who experienced a serious adverse reaction, an unexpected adverse reaction or other adverse reactions not listed in the package insert.

- Presence/absence of adverse event
- Name of adverse event
- Date of occurrence
- Seriousness
- Change in the administration of this drug
- Intervention
- Outcome

- Causal relationship to this drug

If the adverse event is associated with abnormal laboratory values, i.e., clinical laboratory tests, the following information should also be recorded.

- Name of laboratory test
- Site reference value
- Unit
- Date of measurement
- Test results

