For safety events that are considered serious or that are identified in the far right column of the table above that are reportable to Pfizer within 24 hours of awareness, the investigator is obligated to pursue and to provide any additional information to Pfizer in accordance with this 24-hour timeframe. In addition, an investigator may be requested by Pfizer to obtain specific follow-up information in an expedited fashion. This information is more detailed than that recorded on the CRF. In general, this will include a description of the AE in sufficient detail to allow for a complete medical assessment of the case and independent determination of possible causality. Any information relevant to the event, such as concomitant medications and illnesses, must be provided. In the case of a patient death, a summary of available autopsy findings must be submitted as soon as possible to Pfizer or its designated representative.

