6.2. Efficacy Endpoints

- Change in NYHA functional classification
- Change in cardiac biomarker values (NT-pro BNP, BNP, troponin I, troponin T)
- Survival time

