7. HANDLING OF MISSING DATA

If treatment with this drug is continued even after the end of the observation period and the end date of treatment is missing, the end date of observation will be handled as the end date of treatment in this study.

If the seriousness, causal relationship, and action taken and outcome regarding adverse events are missing, these data will be handled as “unknown” for tabulation.

For the efficacy endpoints and laboratory test values, if there is no measurement within the time window for each evaluation time point (Appendix 1), data will be handled as missing, and the missing data will not be complemented.

The strategy for handling data with uncompleted cleaning is described below:

- Items of missing data: The items will be handled as missing (category of categorical variables is “unknown”) for both tabulation and listing.
- Items of inconsistent data: The items will be handled as missing for both tabulation and listing. However, a list of data handling should be prepared separately.
- No signature: Any entry in a case report form without the signature of the contracted physician (including a case report form with the signature of an uncontracted physician only) will be handled as missing for both tabulation and listing. If there is no date of signature in the field for the date of signature or if there is inconsistency in the date entered (e.g., date before the start date of treatment, future date), the entry in the case report form will be regarded as having no signature.

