8.1.4. Analysis of period data (time to event onset)

The median, first quartile, and third quartile will be calculated by the Kaplan-Meier method. For period data which includes interval-censored data, the median, first quartile, and third quartile will be calculated based on the EMICM algorithm. In addition, Kaplan-Meier plots will be prepared.

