8.2.4.3. Survival time

For the period from the start of administration of this drug to the end date of the observation period, the number and proportion of patients experiencing death of any cause and deaths related to cardiovascular events will be tabulated separately. In addition, each event will be summarized as described in Section 8.1.4. In the analysis in Section 8.1.4, data will be censored at the last date of confirmation of survival. If the date of death is unknown and the last date of confirmation of survival and date of death information obtained are known, data will be handled as interval censored. The handling of patients in the survival analysis is outlined below.

Non-English text

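### Deaths of unknown cause share a category with non-cardiovascular deaths, so the planned cardiovascular-death figures may be under-counted and the unknowns are not shown

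*Protocol*

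**What the plan says.** Protocol 8.3.7 asks for survival status, date of death and cause of death. Cause has two options: "cardiovascular event, or others (including unknown". Unknown cause therefore sits inside the residual category.

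SAP 6.2 lists "Survival time" as an efficacy endpoint. Under SAP 8.2.4.3, "the number and proportion of patients experiencing death of any cause and deaths related to cardiovascular events will be tabulated separately", and each event is also summarised by the time-to-event methods of SAP 8.1.4, where "The median, first quartile, and third quartile will be calculated by the Kaplan-Meier method". For that analysis "data will be censored at the last date of confirmation of survival". The readable text does not say how a death in the residual category is treated when the event is cardiovascular death. SAP 8.2.4.4 repeats the efficacy analyses by TTR type and NYHA class.

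The rule in SAP 7 that keeps an unknown category begins "If the seriousness, causal relationship, and action taken and outcome regarding adverse events are missing". It concerns adverse-event attributes and does not mention cause of death.

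There is a second source on each fatal case. Protocol 10.4.2 makes an event that results in death a serious adverse event, and Protocol 10.1 requires every serious adverse event on the CRF. Protocol 8.3.8 records "Name of adverse event" and outcome. Protocol 10.1 adds: "In the case of a patient death, a summary of available autopsy findings must be submitted as soon as possible to Pfizer". No passage links these records to the cardiovascular-death classification.

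**The concern.** The two-way field gives 'cause not known' and 'known not to be cardiovascular' the same code, and the cardiovascular-death analysis treats both as non-events. All patients are treated for a cardiomyopathy, so it would be hard to defend assuming that none of the unknown-cause deaths is cardiac.

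The plan foresees incomplete information on deaths: SAP 8.2.4.3 has an interval-censoring rule for deaths whose date is unknown, and Protocol 8.9 accepts that data taken from charts may be missing. Elsewhere the SAP keeps unknown apart: for TTR genotype and for liver and renal impairment (8.2.2.1), and for adverse-reaction outcome (8.2.3.1.3). Unknown data are also left out of risk ratios (8.2.3.3). Cause of death is handled differently.

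At stake is the cardiovascular-death count, proportion and curve, overall and by subgroup. A reader of the report could not tell from this field how many of the residual deaths had no known cause.

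**Working it through.** **Plan's own figures.** The documents state no death rate, cardiovascular share or unknown-cause share, so there is no figure on this point to reproduce. The probability of about 98% in Protocol 8.5.2 reproduces (exact binomial, at least 10 of 300 at 5.88%: 98.4%) but has no bearing here.

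**Inputs.** From the documents: N = 300 (Protocol 8.5.1). Assumed: D deaths; c, the cardiovascular share of deaths; u, the share of deaths with unknown cause. Known causes are taken as correctly classified.

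**Count and proportion.** Suppose c is the same in known and unknown deaths.

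- True cardiovascular deaths = D × c
- Recorded cardiovascular deaths = D × c × (1 − u)
- Shortfall = D × c × u, which relative to the true count is u

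With D = 60 and c = 0.8, the true count is 60 × 0.8 = 48, or 48/300 = 16.0%.

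| u | Recorded | % of 300 | Shortfall |
|---|---|---|---|
| 5% | 48 × 0.95 = 45.6 | 15.2% | 2.4 |
| 10% | 48 × 0.90 = 43.2 | 14.4% | 4.8 |
| 20% | 48 × 0.80 = 38.4 | 12.8% | 9.6 |

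Over D = 45 to 90, c = 0.6 to 0.8 and u = 5% to 20%, the shortfall runs from 45 × 0.6 × 0.05 / 300 = 0.45 to 90 × 0.8 × 0.20 / 300 = 4.8 percentage points.

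**If the shares differ.** Let q be the cardiovascular share among unknown-cause deaths. The shortfall is q × D × u: zero at q = 0, never negative. With D = 60 and u = 10% there are 6 unknowns, so it lies between 0 and 6 deaths (0 to 2.0 percentage points).

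**What a separate unknown row gains.** Take D = 60, c = 0.8, u = 10%, with 43.2 recorded.

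- Pooled field: the true count can only be placed between 43.2 and 60 (14.4% to 20.0%), a width of 16.8 deaths.
- Unknowns shown: between 43.2 and 43.2 + 6 = 49.2 (14.4% to 16.4%), a width of 6 deaths.

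**Kaplan-Meier curve.** Suppose residual-category deaths are censored, which the readable text does not state. With constant proportional hazards, recorded 1 − KM = 1 − (1 − D/N)^(c(1 − u)), against a true cumulative incidence of c × D/N. Censoring competing deaths pushes 1 − KM upward, against the effect of the pooling.

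| D/N | c | u | True incidence | Recorded 1 − KM |
|---|---|---|---|---|
| 20% | 0.8 | 10% | 16.0% | 14.8% |
| 30% | 0.6 | 5% | 18.0% | 18.4% |
| 30% | 0.6 | 10% | 18.0% | 17.5% |
| 30% | 0.6 | 20% | 18.0% | 15.7% |

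Over D/N = 15%, 20%, 30%, c = 0.6, 0.8 and u = 5%, 10%, 20%, 30% (24 combinations), the net error was downward in all but one: the second row above.

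**The case against.** The strongest reply is that this is a small reporting matter. The study is descriptive (SAP 4), no decision rule depends on cardiovascular death, and all-cause survival is untouched. The category label openly says that it includes unknown causes, and the SAP plans no table of non-cardiovascular deaths that would misstate them. All of this stands and limits the reach of the point.

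Three stronger readings are tempting, and the documents do not support them.

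- *The whole endpoint is biased low.* For the count and proportion this holds only if some unknown-cause death is cardiac and the other classifications are right. The readable text gives no definition of a cardiovascular event and no adjudication rule, so a site could also label an unexplained sudden death cardiovascular. For the curve, the sign can reverse.
- *The size of the error cannot be known.* All-cause and cardiovascular deaths are both tabulated, so their difference caps the under-count. The fatal-event records could narrow it further.
- *Subgroup comparisons are distorted.* Unknown causes might be commoner after transfer or loss to follow-up, but nothing ties either to TTR type or NYHA class, and patients merely lost are censored rather than counted as deaths.

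One limit applies to this check. SAP 8.2.4.3 ends with an outline of patient handling in the survival analysis that is not readable in the available copy. It might state a rule for these deaths. It could not by itself recover a distinction that the cause-of-death field does not capture.

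**Conclusion.** The point holds in a limited form. Unknown-cause deaths are never counted as cardiovascular, so the cardiovascular-death count and proportion are too low by however many of them are cardiac. With equal cardiovascular shares in known and unknown deaths, the relative shortfall equals the unknown share: 5% to 20% on the assumed range. These sizes are illustrations, since the documents supply no rates. The direction for the Kaplan-Meier curve is probably downward but not certain.

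The case for acting is that the bound available from the planned tables is loose, the readable SAP text states no sensitivity analysis, and a tighter bound is cheap to obtain.

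**What to change.** In SAP 8.2.4.3:

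1. Split the deaths recorded in the residual category into known non-cardiovascular and unknown, by data review of the fatal serious adverse event records (event name, outcome, available autopsy summary). Fix the review rule in writing before the split.
2. Show unknown-cause deaths on their own row, overall and by subgroup.
3. Present the cardiovascular-death count, proportion and time-to-event summary twice: unknowns counted as non-cardiovascular, and unknowns counted as cardiovascular.
4. State how deaths not counted as cardiovascular are treated in the time-to-event analysis, so that the direction of any error in the curve can be judged.

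A third CRF category would come too late to help prospectively: Protocol 5 planned the end of observation for September 2023 and database release for November 2024, and SAP version 6.0 is dated January 2025. The recode needs no new category. Protocol 8.2.4 also allows CRFs to be collected where more information is needed.

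The cost is a small review and recode, one table row and one sensitivity analysis. The cardiovascular-death figure would then be reported as a range, and some deaths may stay unknown after review.

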### 8.3.8. Adverse events

Occurrence of adverse events from the start date of administration of this drug to the end date of observation period (or first visit date after the date of discontinuation of this drug) should be confirmed and the following information should be recorded.

Also, further investigation should be separately conducted, if deemed necessary by Sponsor for patients who experienced a serious adverse reaction, an unexpected adverse reaction or other adverse reactions not listed in the package insert.

- Presence/absence of adverse event
- Name of adverse event
- Date of occurrence
- Seriousness
- Change in the administration of this drug
- Intervention
- Outcome

- Causal relationship to this drug

If the adverse event is associated with abnormal laboratory values, i.e., clinical laboratory tests, the following information should also be recorded.

- Name of laboratory test
- Site reference value
- Unit
- Date of measurement
- Test results

#### 8.4. Data sources

In this study, the investigators transcribe the necessary information from the medical record under daily medical practice in accordance with the full protocol.

#### 8.5. Study size

##### 8.5.1. Sample size

A total of 300 patients will be included in the safety analysis set (SAS).

##### 8.5.2. Rationale

The number of patients with ATTR-CM in Japan is estimated to be approximately 750. Of these, the proportion of patients who actually received the definitive diagnosis and were prescribed with this drug was estimated to be approximately 40% (approximately 300 patients). As a result, the target sample size was set at 300 subjects from the viewpoint of feasibility. The target sample size of 300 subjects was comparable to the active drug group (264 patients) in the global phase 3 study, and from this point of view, it is considered possible to confirm the safety and effectiveness of the drug to some extent.

If the number of subjects in the SAS is 300, at least 10 subjects with hepatotoxicity can be observed with a probability of approximately 98%, assuming that the true incidence of hepatotoxicity with the lowest incidence based on Studies B3461028 and B3461045 is 5.88% for infections, hypersensitivity reactions, and hepatotoxicity, all of which are important potential risks that can be reviewed.

#### 8.6. Data management

##### 8.6.1. Case report forms (CRFs)/Electronic data record

As used in this protocol, the term CRF should be understood to refer to either a paper form or an electronic data record, or both, depending on the data collection method used in this study.

A CRF is required and should be completed for each included patient. The completed original CRFs are the sole property of Pfizer and should not be made available in any form to third parties, except for authorized representatives of Pfizer or appropriate regulatory authorities, without written permission from Pfizer. The investigator shall ensure that the CRFs are securely stored at the study site in an encrypted electronic and/or paper form and will be password protected or secured in a locked room to prevent access by unauthorized third parties.

The investigator has ultimate responsibility for the collection and reporting of all clinical, safety, and laboratory data entered on the CRFs and any other data collection forms (source documents) and ensuring that they are accurate, authentic/original, attributable, complete, consistent, legible, timely (contemporaneous), enduring, and available when required. The CRFs must be signed by the investigator or by an authorized staff member to attest that the data contained on the CRFs are true. Any corrections to entries made in the CRFs or source documents must be dated, initialed or stamped "correction seal", and explained (if necessary) and should not obscure the original entry.

The source documents are the hospital or the physician's chart. In these cases, data collected on the CRFs must match those charts.

#### **8.6.2. Record retention**

The records related to this study should be retained at the study site until the End of Study Letter by Pfizer is received or during the period defined by the study site, whichever is longer.

#### **8.6.3. Data collection method (EDC)**

The data for this study will be collected and confirmed by using the electronic system on the internet designed for collecting post-marketing survey data (Electronic Data Capture, EDC).

#### **8.6.4. Patient registration (EDC)**

The investigator will enter information on the patient registration screen of EDC (the registration form) and save the data. Patient registration will be performed immediately after the first administration of this drug.

If information in the registration form require confirmation, the investigator may be requested to perform follow-up survey and respond to the query. Registration will be fixed after the query is resolved.

#### **8.6.5. Points to consider for completion, revision, and submission of CRF (EDC)**

##### **8.6.5.1. Data entry**

The investigator should confirm the survey items, and enter the data into EDC based on medical records.

*PFIZER CONFIDENTIAL*

*CT24-WI-JPN-GPSP01-RF09 7.0 Non-Interventional Study Protocol Template for Secondary Data Collection*

*Study 15-Sep-2022*

*Page 22 of 39*

#### **8.6.5.2. Data revision**

Upon receiving query from Sponsor on the contents of the CRF (follow-up survey), the investigator will again confirm the contents of medical records, and as required, correct relevant sections and save the data.

#### **8.6.5.3. Submission**

After data entry and revision are completed, CRFs should be signed electrically by the investigator following confirmation of entry and follow-up survey.

#### **8.6.6. Data collection method (paper CRFs)**

In this study, the data will be collected and confirmed by using paper CRFs, only when the EDC is not available under unavoidable circumstances at the study sites.

#### **8.6.7. Patient registration (paper CRFs)**

The investigator will complete the registration form provided by Sponsor for patients receiving this drug and submit the form to Patient Registration Center via FAX. Patient registration will be performed immediately after the first administration of this drug.

1. After the patient was registered, "the notification of the patient registration" will be sent by FAX. Investigator will maintain the notification at the site.
2. If information in the registration form require confirmation, the investigator may be requested to perform follow-up survey. For follow-up survey, "follow-up survey request form" and "registration form (copy)" will be sent from the Registration Center to the investigator by FAX.

#### **8.6.8. Points to consider for completion, revision, and submission of CRF (paper CRFs)**

##### **8.6.8.1. Data entry**

The investigator should confirm the survey items, complete the CRF based on medical records and other medical records such as relevant test results, using an ineffaceable ink such as ballpoint pen.

##### **8.6.8.2. Data revision**

Upon receiving query from Sponsor on the contents of the CRF (follow-up survey), the investigator will again confirm the contents of medical records, and as required, correct relevant sections and resubmit the form.

##### **8.6.8.3. Submission**

After data entry and revision are completed, CRFs should be submitted by the investigator to the designated address following confirmation of entry and follow-up survey.

#### 8.6.9. All cases survey registration

1. The investigator will confirm whether all patients receiving this drug before 31 March 2021 are registered. The investigator should sign and affix a seal to the all-cases survey confirmation sheet and submit it to the site staff. E-mail etc. can be also used.
2. Any unregistered patients should be promptly registered.

#### 8.7. Data analysis

##### 1. Definition of analysis set

The SAS consists of a full analysis set (FAS) that is as closer as possible to all patients who received this drug. The effectiveness analysis set consists of patients included in the SAS considered evaluable for efficacy. The details will be described in the separately prescribed Statistical Analysis Plan (SAP). Safety and effectiveness should be evaluated using all data collected during the observation period without classifying the data into Vyndaqel and Vynmac unless otherwise specified.

##### 2. Method of analysis

- Analysis for safety evaluation

Events possibly related to this drug are considered as adverse drug reactions (ADRs). The number of patients with ADRs and the proportion  $[(\%): \text{number of patients with ADRs} / \text{number of patients included in the SAS}]$  will be calculated.

Based on the above method, important missing information and important potential risks will also be evaluated.

- Analysis for effectiveness evaluation

Time course of changes in the following items from the start of administration of this drug will be recognized.

- NYHA Functional Classification
- Cardiac biomarker values (NT-pro BNP, BNP, troponin I, and troponin T)

In addition, survival time analysis will be performed using survival information obtained up to 30 months after the start of administration.

- Subset analysis

The analysis by variant genotype and NYHA Functional Classification will be also performed for the above safety and effectiveness evaluations.

Also, the onset status of adverse reactions will be evaluated for each product (Vyndaqel or Vynmac) during the treatment period until the first switching to Vynmac for Vyndaqel and during the treatment period after the first switching to Vynmac for Vynmac.

Detailed methodology for summary and statistical analyses of data collected in this study will be documented in the SAP, which will be dated, filed and maintained by the Sponsor. The SAP may modify the plans outlined in the full protocol; any major modifications of primary endpoint definitions or their analyses would be reflected in a full protocol amendment.

